## A. Introduction and Background

SARS-CoV-2 is a high contagious virus that has infected millions of Americans and is disproportionately impacting the Latinx population. Nationally, Latinx people are hospitalized with COVID-19 infections at four times the rate of Whites. This disparity is notable in Oregon, where Latinxs represent approximately 44% of COVID-19 cases, while representing only about 13% of the state's population. Therefore, there is an urgent need to reach Oregon's Latinx community with public health and prevention messages that are culturally-relevant, address community concerns, and are delivered through appropriate information channels in order to increase testing rates and ultimately, reduce the spread of infection and mortality rates.

The overall goal of the proposed research is to implement a culturally-tailored community outreach and testing program to increase the reach, access, uptake, and impact of testing in Latinx communities in Oregon. Our project has received funding to provide SARS-CoV-2 testing across the state of Oregon from two sponsors: National Institutes of Health (NIH) (EPICS #30680 and EPICS #29424) and Oregon Health Authority (OHA) (EPICS #31138). NIH funded events include a individual-level data collection component (participant survey) to address study aims. OHA funded events will not include any individual-level data collection, and will only collect de-identified protected health information.

## B. Specific Aims/Study Objectives

The overall goal of our proposed research is to implement a culturally-tailored community outreach and testing program to increase the reach, access, uptake, and impact of testing in Latinx communities in Oregon. This project will fully integrate with the NIH Rapid Acceleration of Diagnostics (RADx) consortium and its Coordination and Data Collection Center (CDCC). With guidance and leadership from our Latinx Community and Scientific Advisory Board, we will launch the proposed testing program which will result in 36 community testing sites to serve Latinx communities. For the proposed research activities, we will test the following questions:

- 1) Do culturally-informed interventions ('Promotores') increase test rates and health behaviors?
  - a. Community-level intervention to increase participation in testing: Evaluate whether 'Promotores de Salud,' a culturally-tailored outreach intervention that includes psychoeducation, information support, and motivational strategies to address barriers, results in more tests completed and more sites testing at full capacity, as compared to basic community-level outreach services.
  - b. Individual-level booster intervention to change future health behavior: Examine whether a brief, individual-level 'Promotores de Salud' intervention held during a testing event (compared to distribution of a pamphlet only) results in greater use of strategies that reduce transmission at the community and individual level. Individual moderators (e.g., substance use, perceived threat, health literacy, social determinants) will also be examined. We further hypothesize that this intervention will increase future test rates through repeat testing visits and

through ‘snowball’ recruitment of friends and family to attend future testing events.

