## C. Methods, Materials and Analysis

Overall Study Design: We will partner with community organizations to administer SARS-CoV-2 tests at organized, planned testing events located in communities across Oregon. Sample collection will occur in counties across Oregon and we will collaborate with county public health agencies to determine sites. Samples will be collected using services as usual using a standardized intake form and standardized, EUA authorized sample collection approaches. Data used to evaluate the efficacy of interventions will involve de-identified participant data at the level of the testing site. This study is a randomized clinical trial to test whether ‘Promotores,’ community health workers who deliver culturally-informed set of outreach, education, and engagement interventions, will result in an increase in testing utilization and health behaviors in Latinx communities.

Randomization will occur at the site level such that 18 sites will be randomized to receive the Promotores intervention and 18 will be randomized to receive services as usual. Services as usual include outreach by county public health and community-based organizations (fliers, radio ads, social media, etc.). The promotores intervention includes targeted outreach to Latinx community members and educational direct interactions with participants and distribution of a pamphlet, with the goal of increasing health behaviors and encouraging additional/future testing. The UO will provide support to community-based organizations to employ and train these promotores to assist with recruitment. The promotores will include Spanish speakers, across cultural contexts, living and working in, and intricately connected to, the target community.

- **Outreach as usual description**
  - Basic outreach materials document (flyers, social media posts, radio announcements, etc.)
  - Flyer to promote health behaviors
  - These documents may be modified or not used at all by community stakeholders as they may have other documents they are already using for outreach and health education—these materials are intended to be used for counties who do not have existing or preferred materials
  - See 04c.Services as Usual Materials
- **Promotores intervention description**
  - Basic outreach and flyer to promote health behaviors plus the outlined outreach and health behaviors promotores approaches
  - Promotores training will be provided by the study team
  - See 4d. Promotores Training Outline

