- 3. Anonymous participant interview** will be collected from a sub-set of randomly selected individuals at NIH-funded testing events who are age 18 years or older. We will invite approximately 15 individuals to participate in a brief anonymous interview (5-8 open-ended questions) with a study staff member at our testing events. Anonymous interview data will assist with informing the study about individual behaviors related to attending testing events. We will audio record these interviews for transcription. All audio recordings will be destroyed after transcription activities are complete. A standardized recruitment script will be used, which will provide information about the purpose of the interview and permission for audio recording. Individuals will be compensated with a \$15 gift card for completion of this interview. These anonymous interviews will not be used as research data, and are only to provide feedback on the testing events. This aspect of the study has now been completed.
- 4. Promotores activities.** Promotores will be recruited after receiving contact information from the community-based organization employing each promotor. They will be invited to participate in the promotores training and, for NIH-funded testing events, they will be asked to complete the informed consent and survey asking about their demographics and personality during the course of the promotores training. Promotores will also be invited to participate in a focus group interview about their experiences delivering the intervention and opinions on the project and content delivery. There is no monetary incentive for participation. The only inclusion criteria will be that the individual must be a promotor funded by the present study.
- 5. Community Based Organization general outreach activities.** A monthly email will be sent to the executive director of each CBO participating in the NIH-funded testing events to complete a survey on general outreach activities. Completion of the survey is part of the requirements for receiving CBO funding.

For data analysis, we will employ standard normal theory generalized linear modeling analysis of covariance fractional factorial analyses using pre-post assessment scores for site and individual level outcomes.

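### Aim 1b claims an on-site booster effect against a pamphlet, but the only randomisation described compares the whole Promotores package with an unstandardised services-as-usual arm

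*Protocol*

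**What the plan says.** Protocol section B poses two separate questions. Question 1a concerns community outreach by promotores and asks whether it "results in more tests completed and more sites testing at full capacity, as compared to basic community-level outreach services". Question 1b concerns a brief individual promotores "intervention held during a testing event (compared to distribution of a pamphlet only"), judged on behaviours that reduce transmission.

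Protocol section C gives one allocation: "18 sites will be randomized to receive the Promotores intervention and 18 will be randomized to receive services as usual". It describes the active arm as a bundle: "The promotores intervention includes targeted outreach to Latinx community members and educational direct interactions with participants and distribution of a pamphlet". Of the outreach materials and health-behaviour flyer supplied for usual services it says: "These documents may be modified or not used at all by community stakeholders". The reason given is that local groups may already have materials of their own. Section H sums up usual services as a health-behaviour flyer.

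Four other places bear on the point:

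- Section D, item 2, expects up to 1,800 survey participants who received the promotores intervention and up to 1,800 with services as usual.
- The last paragraph of section D announces "generalized linear modeling analysis of covariance fractional factorial analyses" for site and individual outcomes, without naming the factors.
- Section G, discussing social risk, says that half of those attending an intervention site will be offered the intervention. It does not say how that half is chosen.
- SAP section 4.3 sets its individual-level aims (Aims 2 and 3) as before-to-after change among people in the intervention group. The group contrast in its Aim 1 model is type of site location.

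**The concern.** Question 1b names a component and a comparator, so it promises the effect of a short on-site conversation over and above a pamphlet. The described allocation switches outreach, conversation and pamphlet on together for a whole site. A difference between arms in attendees' behaviour could then arise from the outreach they met beforehand, from the conversation, from a different mix of people attending, or from differences in printed material.

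If a positive difference were read as the answer to 1b, the result would suggest that the on-site talk works alone. A programme could then fund the talk and drop the outreach on evidence that does not separate them. A larger sample does not help, because the difficulty lies in what was allocated together.

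**Working it through.** **Inputs.** 36 sites (section B); 18:18 by site (section C); up to 3,600 surveys, up to 1,800 per condition (section D, item 2); half of attendees offered the intervention (section G); ICC 0.30, one-month retention 50%, alpha 0.05 and power 0.80 (SAP 4.3). The documents give no power figure for the 1b contrast, so there is none to reproduce.

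**1. The stated survey split.** Assuming equal numbers at all 36 sites:
- 3,600 / 36 = 100 per site.
- Whole-site exposure: 18 × 100 = 1,800 exposed and 1,800 not, which matches section D.
- Half exposed at intervention sites: 0.5 × 18 × 100 = 900 exposed and 3,600 − 900 = 2,700 not, which does not match.

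The stated figures therefore fit whole-site exposure better. This is supporting evidence only, because both 1,800s are ceilings and surveys are taken only at NIH-funded events.

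**2. Estimability.** Take the columns intercept, outreach and booster for 36 sites × 100 people.
- Everyone at an intervention site gets the booster: the outreach and booster columns are identical, rank 2 of 3. The booster effect is not identified.
- Half at each intervention site get it: rank 3 of 3. The effect is estimable, but is protected from confounding only if the half was chosen at random.

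**3. What the arm difference contains.** On an additive scale,

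D = O + hB + (1 − q)P + S

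where O is the outreach effect on behaviour, B the booster effect, h the share of intervention-site attendees who get the booster, P the pamphlet effect, q the share of usual-services attendees given that pamphlet or an equivalent, and S the difference due to who attends. With h = 1, only O + B appears. With h = 0.5, D still mixes O and B, and only a comparison inside intervention sites could separate them.

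Illustration with assumed values B = 0, S = 0, O = 0.2 SD, P = 0.1 SD:
- q = 1: D = 0.20
- q = 0.5: D = 0.20 + 0.5 × 0.1 = 0.25
- q = 0: D = 0.20 + 0.1 = 0.30

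All three would look like support for 1b although the booster does nothing. The documents do not give q.

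**4. What each design could detect.** These figures are illustrative: they assume 100 surveys per site and a two-sided test, and borrow the SAP's ICC and retention, which were set for a different design. MDE = (1.96 + 0.84) × √(2 × variance × design effect / n per group).
- Package, 18 v 18 sites, 900 v 900 retained: design effect 1 + 49 × 0.30 = 15.7; MDE = 2.80 × √(2 × 15.7 / 900) ≈ 0.52 SD (0.25 to 0.60 for ICC 0.05 to 0.40).
- Booster randomised within the 18 intervention sites, 450 v 450 retained, variance 1 − 0.30 = 0.70: MDE = 2.80 × √(2 × 0.70 / 450) ≈ 0.16 SD (0.15 to 0.18 over the same ICC range).

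The two designs answer different questions with very different precision, so the protocol must say which one was run.

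**The case against.** The strongest reply is section G. If half of the attendees at an intervention site are offered the intervention, outreach and booster do not always coincide. The fractional factorial wording in section D could be the trace of that second factor. This stands in part. A reader might infer that the booster effect is proven to be unidentifiable at any sample size; the documents do not support that, because section G contradicts the premise that the components always occur together. But section G gives no rule for choosing the half, section C describes randomisation of sites only, and the counts in section D sit better with whole-site exposure. So section G shows that the text needs reconciling; it does not rescue 1b.

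A reader might also infer that some usual-services attendees received no pamphlet. The text does not show this. Section C describes local groups using their own materials instead, and section H describes usual services as a flyer. What stands is that the comparator is not standardised.

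A third inference is that repeat visits and referrals prompted by the on-site contact contaminate 1a. Section C makes further testing a goal of the arm, so this is an intended mechanism, and a package reading of 1a already covers it.

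Finally, 1b is not the primary outcome. Section C makes site-level testing rates of Latinx individuals primary, and both the parent question in section B and the benefit statement in section H are about the intervention as a whole. That limits the damage but does not give 1b a design.

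**Conclusion.** The point holds conditionally. Under the only randomisation described, the booster effect and the outreach effect are aliased (rank 2 of 3). The arm difference in attendees' behaviour estimates neither, and it also carries any effect of outreach on who attends, since survey participants are recruited at the event. In the illustration, a difference of 0.20 to 0.30 SD arises with a booster effect of zero.

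The conclusion rests on section C being the complete account of allocation. A documented random allocation within intervention sites would make the booster effect estimable and change the conclusion.

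The trial does not lose its randomised comparison. The effect of the whole package against services as usual is estimable by site arm, and the primary site-level outcome stands on that footing. What lacks support is a conclusion specific to the booster or to outreach. The SAP does not fill the gap, because it holds no booster-versus-pamphlet comparison and no between-arm model for 1b.

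**What to change.** First reconcile Protocol sections B (1a and 1b), C, D (item 2 and last paragraph) and G on whether any allocation was made within intervention sites.

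If a randomised within-site allocation was used and can be documented, describe its unit, method and numbers, name the factors, and add the matching analysis to the SAP.

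Otherwise:

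- Restate 1a and 1b as effects of the whole Promotores package against services as usual, on site test counts and on attendees' health behaviours respectively.
- Withdraw conclusions specific to the booster or to outreach.
- Remove the fractional factorial wording from section D and the half-of-attendees statement from section G. Do this only after the reconciliation, since they may record something that was intended.
- Specify the 1b analysis as a between-arm comparison by randomised site arm with clustering by site, and state as a limitation that attendees are recruited after outreach.
- Describe the comparator as services as usual with locally chosen materials.

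Handing the study flyer to every attendee at all sites is not needed once 1b is a package contrast. It would also alter usual care in a study that appears to be under way, since the protocol reports the anonymous interviews as complete.

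The cost is rewording and one added model. The sponsor gives up a component-specific claim.

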## C. Methods, Materials and Analysis

Overall Study Design: We will partner with community organizations to administer SARS-CoV-2 tests at organized, planned testing events located in communities across Oregon. Sample collection will occur in counties across Oregon and we will collaborate with county public health agencies to determine sites. Samples will be collected using services as usual using a standardized intake form and standardized, EUA authorized sample collection approaches. Data used to evaluate the efficacy of interventions will involve de-identified participant data at the level of the testing site. This study is a randomized clinical trial to test whether ‘Promotores,’ community health workers who deliver culturally-informed set of outreach, education, and engagement interventions, will result in an increase in testing utilization and health behaviors in Latinx communities.

Randomization will occur at the site level such that 18 sites will be randomized to receive the Promotores intervention and 18 will be randomized to receive services as usual. Services as usual include outreach by county public health and community-based organizations (fliers, radio ads, social media, etc.). The promotores intervention includes targeted outreach to Latinx community members and educational direct interactions with participants and distribution of a pamphlet, with the goal of increasing health behaviors and encouraging additional/future testing. The UO will provide support to community-based organizations to employ and train these promotores to assist with recruitment. The promotores will include Spanish speakers, across cultural contexts, living and working in, and intricately connected to, the target community.

- **Outreach as usual description**
  - Basic outreach materials document (flyers, social media posts, radio announcements, etc.)
  - Flyer to promote health behaviors
  - These documents may be modified or not used at all by community stakeholders as they may have other documents they are already using for outreach and health education—these materials are intended to be used for counties who do not have existing or preferred materials
  - See 04c.Services as Usual Materials
- **Promotores intervention description**
  - Basic outreach and flyer to promote health behaviors plus the outlined outreach and health behaviors promotores approaches
  - Promotores training will be provided by the study team
  - See 4d. Promotores Training Outline

Data points to assess testing site utilization and the health behaviors will include the following:

1. **De-identified protected health information** (from intake forms) from those who engaged in testing (age 3 and older)
  - a. After testing occurs, researchers will have access to de-identified data prepared by the UO’s CLIA laboratory. The data will include four protected health identifiers, site zip code, participant zip code, testing date, and SARS-CoV-2 test result. It will also include demographic data this is not protected health information such as CDC age range, race, and ethnicity. These data will be used to assess outreach activities aimed at increasing participation of Latinx community members in SARS-COV-2 testing. Primary outcomes will be site-level testing rates of Latinx individuals.
  - b. In addition, the study team will record and have access to a list of testing site addresses and testing date, that will be merged with the aggregate file provided by the CLIA laboratory.

2. **Individual level survey data**, collected at NIH-funded testing events from a subset of 3,600 adult participants (age 15 and older).
  - a. Surveys will contain information including demographic information, including address, phone number, and email. This is being collected to link the HIPAA data that we are collecting from the UO CLIA laboratory, in addition to allowing researchers to see if individuals are getting tested in close proximity to their residence. Researchers are looking at population density of Latinx individuals in an area compared to the proportion of Latinx people who attend the testing events. Additionally, the survey will include information about health behaviors to prevent the spread of COVID-19. These data will be collected using an electronic survey that participants can complete on their smartphone, or using an iPad provided on site. If preferred by the participant, the survey may be completed on paper. If the participant prefers or as is needed, the survey items will be read by a field team member, who is bicultural and bilingual. Surveys will be available in Spanish and in English.
  - b. Individuals who are willing to participate in the survey will be asked in the first survey how they prefer to complete the follow-up survey. They will be able to select to receive a text message with a follow-up survey link, email with a follow-up survey link or a paper survey by postal mail with a pre-paid envelope to return the survey, one month later. For participants who prefer, the one-month survey will be conducted by telephone. Each survey will take approximately 30 minutes to complete.
  - c. As part of standardized testing protocols, participants will complete an intake form. As part of the consent and assent process, they will provide consent or assent to share their identifiable protected health information with the research team. Their intake data will be linked to the survey data.
  - d. Survey data will be collected in-person at testing sites, requiring direct interaction with participants.
3. **Anonymous participant interview**. A random set of individuals will be asked to participate in the anonymous interview following testing. Participants who verbally agree to this component will be directed to meet with a study staff member at a testing event after they complete the testing event activities. A study staff member will verbally consent the participant using the consent script. This aspect of the study is now complete.
4. **Promotores activities**. In addition to non-human subjects activities (e.g., reporting on training, outreach activities and interactions with participants), promotores will be asked to complete two questionnaires to provide some demographic information, information about their personality traits (e.g., conscientiousness), and feelings about participating as a Promotor/a on this project. They will be asked to complete an electronic informed consent before participating in the interviews.
  - a. The first survey will directly follow the promotores training and will ask basic demographic information and information on their personality traits.
  - b. The second interview will be in the format of a focus group and will ask questions about their experience as a promotor/a and their perspectives on the intervention.
5. **Community Based Organization general outreach activities**. The executive director of each CBO that receives promotores funding will provide a monthly report on the general outreach strategies conducted by the organization. This is a condition of receiving funding, but reports will be included in research reports such as peer reviewed journal articles.

